8.6.4.3 Cumulative oral/IV steroid dose during the duration of current COPD exacerbation

A descriptive summary table will be presented by treatment regimen for the cumulative oral/IV steroid dose (prednisone equivalent dose) during the duration of current COPD exacerbation. The cumulative prednisone dose will be compared between treatment regimens using a one-way ANOVA test, and the associated two-sided p-value will be reported in the summary table.

Should the normality assumptions for cumulative prednisone dose not be met (the skewness and kurtosis measurements will be considered as supportive indicators), the relationship between cumulative prednisone dose and treatment regimen will be tested using the non-parametric approach of Kruskal-Wallis test (or Wilcoxon Rank-Sum test for pairwise treatment regimens).

8.6.4.4 Change in inflammatory blood biomarkers

Blood biomarkers parameters (IL-6, TNF- α , Fibrinogen, Hs-CRP, MPO) will be measured on days 1 to 7, days 10 and 14, and at Week 8, 12 and 26.

Biomarker data are reported as concentration results, measured using a specific assay with a working range defined by the two limits: Lower limit of quantification (LLOQ) and Upper limit of quantification (ULOQ). Values which fall below the LLOQ or above the ULOQ are reported as $< \text{LLOQ} * \text{dilution factor}$ (dilution factor: if sample diluted and concentration measured still below LLOQ) and $> \text{ULOQ} * \text{dilution factor}$, respectively.

All results for the above biomarker parameters, if collected, will be summarised on the ITT and PP populations by descriptive statistics stratified by treatment regimen and time-point, and including the geometric mean and coefficient of variation. Changes in the biomarker concentrations from baseline (Study Day 1 pre-dose) will be also summarised at each post-baseline time-point.

In the summary table, the frequency (n, %) of values below the LLOQ and above the ULOQ, respectively, will be included.

In case of censored values (values below the LLOQ and/or values above the ULOQ), the values reported as $< \text{LLOQ}$ will be imputed as $0.5 * \text{LLOQ}$ and values reported as $> \text{ULOQ}$ will be imputed as $1.5 * \text{ULOQ}$.

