- 7 There will be sparse PK sampling in all subjects to be taken on any 2 of the 3 dosing occasions (Days 1, 3, or 5): one sample to be taken pre-dose, one sample taken 0-2 h post-dose, one sample taken 4-8 hours post-dose, and one sample no earlier than 12 hours post-dose. ECG will be taken at approximately the same time as with PK sample. ECGs should be taken before the PK sample.

A Symbol of Excellence

Statistical Analysis Plan (SAP)

- 8 Spirometry will be taken 'on bronchodilator' and ideally in the morning. For an individual spirometry should be taken at approximately the same time of day (during the acute phase \pm 1 hour and in the stabilisation phase \pm 2 hour window). Ideally this will be taken at least 1 hour after regular long acting bronchodilators and 30 minutes after short acting bronchodilator medication. Time of last short and long acting bronchodilators will be documented.
- 9 Spirometry at Screening should be performed 'on bronchodilator'. This will be taken after any regular long acting bronchodilator administration and 30 minutes after short acting bronchodilator medication.
- 10 Perform BMI and 6MWT at Day 14. BODE will then be calculated.
- 11 Please refer to the Laboratory Manual for clarification of whether the biomarker is to be analysed in either serum or plasma.
- 12 If the subject is discharged before Day 7, they will return to the hospital daily for assessment.
- 13 If screening and Day 1 occur on different days spirometry will be repeated on day 1 before dosing with study treatment and result obtained on day 1 may be used as baseline.
- 14 If historical spirometry data within last 12 months does not include pre and post SABA value this should be obtained during the stabilisation phase, for demographic purposes.
- 15 Physical examination at screening should include a minimum of chest, cardiovascular and abdominal examination. At all other time points a minimum of chest auscultation is required. Additional examination is at the discretion of the Investigator as indicated by the subjects' clinical condition.
- 16 A gynaecological history should be taken (from females only) with subjects specifically asked about vaginal bleeding, discharge or pain. Any new vaginal bleeding (other than normal menstruation), vaginal discharge or pain after dosing should be investigated by vaginal examination and any required specialist assessment.

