8.7.2 Clinical laboratory evaluations

Haematology, blood chemistry, and urinalysis will be conducted at Screening, on Days 1, 3, 5, 7, 10 and 14, and at each visit in the Stabilisation Phase.

Haematology, blood chemistry and pregnancy tests done at the Screening visit of the study should be sent to both the local laboratory and central laboratory for analysis. Haematology, blood chemistry and pregnancy done at all other visits of the study should be sent only to the central

laboratory for analysis, with the exception of urine dipstick pregnancy test that should be done at the local laboratory. The following laboratory parameters will be assessed:

- Blood chemistry:
 - Creatinine
 - Blood urea nitrogen [BUN]
 - Fasting serum glucose
 - Aspartate aminotransferase [AST]
 - Alanine aminotransferase [ALT]
 - Gamma-glutamyl transpeptidase
 - Total bilirubin
 - Albumin
 - Chloride
 - Calcium
 - Phosphorous
 - Uric acid
 - Total protein
 - Sodium
 - Potassium.
- Haematology:
 - Red Blood Cell Count [RBC]
 - White Blood Cell Count [WBC]
 - Neutrophils
 - Lymphocytes
 - Monocytes
 - Eosinophils
 - Basophils
 - Haemoglobin
 - Haematocrit
 - Platelets
 - INR (not required during the Stabilisation Phase)
 - Prothrombin time (not required during the Stabilisation Phase).
- Urinalysis:
 - Specific gravity
 - pH
 - Protein
 - Glucose
 - Blood.

- Pregnancy test:
 - Serum β -HCG
 - Urinary pregnancy test.

For the purposes of summarisation in both the tables and listings, all clinical laboratory data will be reported in Standard International (SI) units.

If a lab value is reported using a nonnumeric qualifier e.g., less than (<) a certain value, or greater than (>) a certain value, the given numeric value will be used in the summary statistics, ignoring the nonnumeric qualifier.

Descriptive statistics will be presented for quantitative clinical laboratory parameters for each treatment regimen and time-point. Similarly, changes from baseline will be summarised. Values outside the normal range will be categorised as H (above the normal range) or L (below the normal range) based on the laboratory's reference range and these will be flagged in the individual data listings along with the Investigator's assessment.

In addition, the number and percentages of subjects with laboratory values for liver function and enzymes of clinical concern⁷ as follows will be presented descriptively per treatment regimen during the Acute Exacerbation Phase.

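### The biomarker imputation rule omits the dilution factor carried by the reported limit, so an over-range diluted sample can be set below a value it is known to exceed

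*SAP*

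**What the plan says.** SAP section 8.6.4.4 covers IL-6, TNF-alpha, fibrinogen, hs-CRP and MPO. It does four things that matter here.

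- It defines LLOQ and ULOQ as the two limits of the working range of the assay.
- It sets the reporting convention. The sentence beginning "Values which fall below the LLOQ or above the ULOQ are reported as" gives below LLOQ x dilution factor at one end and above ULOQ x dilution factor at the other. A parenthesis explains the factor for the low end: "dilution factor: if sample diluted and concentration measured still below LLOQ".
- It sets the imputation. The sentence beginning "In case of censored values (values below the LLOQ and/or values above the ULOQ), the values reported as" assigns 0.5 x LLOQ to values reported below LLOQ and 1.5 x ULOQ to values reported above ULOQ. No dilution factor appears.
- It plans summaries by regimen and time-point, "including the geometric mean and coefficient of variation. Changes in the biomarker concentrations from baseline (Study Day 1 pre-dose) will be also summarised". The number and percentage of values outside each limit are also tabulated.

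Protocol section 11.2.7 lists only the analytes and time-points. No other section of either document carries the dilution factor into the imputation.

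**The concern.** A diluted sample that is still over range has a known lower bound, namely the assay limit times the dilution factor. A substituted value should respect that bound. The rule as written uses the undiluted assay limit, so it can assign a concentration that the laboratory result has already excluded. It can also place that sample below a less extreme diluted sample that was successfully quantified.

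What is at stake is whether the biomarker tables can be believed at the top of the range. A few very high concentrations pulled down can move an arithmetic mean, a geometric mean and a coefficient of variation, and can change the sign of an individual change from Baseline.

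**Working it through.** There is no stated figure to reproduce. The check is algebraic.

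**Inputs.** From SAP 8.6.4.4: the reported bound at the high end is d x ULOQ and the imputed value is 1.5 x ULOQ; at the low end they are d x LLOQ and 0.5 x LLOQ. The dilution factor d is not given in either document, so d = 2, 5 and 10 are assumptions chosen to show a range.

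**High end.** Imputed value / known lower bound = (1.5 x ULOQ) / (d x ULOQ) = 1.5/d. This is below 1 whenever d > 1.5. At d = 1.5 the imputed value equals the bound, although the true value lies strictly above it.

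| d | Bound (x ULOQ) | Imputed, as written (x ULOQ) | Imputed / bound | Imputed from reported limit (x ULOQ) |
|---|---|---|---|---|
| 1 | 1 | 1.5 | 1.50 | 1.5 |
| 2 | 2 | 1.5 | 0.75 | 3 |
| 5 | 5 | 1.5 | 0.30 | 7.5 |
| 10 | 10 | 1.5 | 0.15 | 15 |

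**Rank order and sign of change (assumed d = 5).** A sample quantified after dilution at 3 x ULOQ ranks above one reported as over 5 x ULOQ, because the latter is set to 1.5 x ULOQ.

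- Baseline quantified at 3 x ULOQ, later visit over range: computed change 1.5 - 3 = -1.5 x ULOQ. The true change exceeds 5 - 3 = +2 x ULOQ.
- Baseline over range, later visit quantified at 3 x ULOQ: computed change 3 - 1.5 = +1.5 x ULOQ. The true change is below 3 - 5 = -2 x ULOQ.

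The sign reverses in both cases, in opposite directions.

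**Geometric mean.** If a share s of the samples in a cell is over range at a single dilution factor d, the geometric mean under the rule as written, divided by that under the reported-limit rule, is d^(-s). The share is also an assumption.

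| s | d = 2 | d = 5 | d = 10 |
|---|---|---|---|
| 5% | 0.966 | 0.923 | 0.891 |
| 10% | 0.933 | 0.851 | 0.794 |
| 20% | 0.871 | 0.725 | 0.631 |

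**Low end.** Imputed value / reported upper bound = (0.5 x LLOQ) / (d x LLOQ) = 0.5/d, which is 0.25, 0.10 and 0.05 for d = 2, 5 and 10. It never exceeds 0.5 for d of 1 or more, so the bound is respected. The value is simply no longer half of the reported limit: it is 1/d of that half.

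**The case against.** The strongest reply is that LLOQ and ULOQ in the imputation sentence are shorthand for the reported limits just described, so an analyst would scale the reported number and obtain the right value. That is a possible intention, and it would remove the problem. But the section defines the two terms as assay limits and writes the dilution factor out explicitly where it wants it. A third reading, that the rule covers only undiluted results, leaves diluted out-of-range results with no rule. The text needs amending on any of these readings. By contrast, the rule for qualified clinical laboratory values in SAP 8.7.2 works from the reported number itself ("the given numeric value will be used in the summary statistics, ignoring the nonnumeric qualifier"), so it cannot fall below a reported lower bound.

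The other replies concern importance, and they stand. These are exploratory endpoints. Section 8.6.4.4 plans no model, test or decision rule, and protocol 13.5.1 treats all analyses as exploratory. The out-of-range counts are already tabulated, SAP 8.1.3 adds the median, which is less sensitive to the tail, and SAP 8.1.9 provides listings that include derived data. None of these corrects the imputed values, but they limit the damage.

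Several stronger inferences are tempting and are not supported:

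- **That over-range samples cluster at Baseline, so the fall from Baseline is understated.** Protocol 9.2 says inflammation is most intense early, which makes this plausible. Nothing in the documents shows that early samples exceed the assay range after dilution, and the worked example shows that the error can go either way.
- **That the comparison between regimens is biased.** The same rule applies to all three arms, and nothing suggests that censoring differs between them.
- **That the trial's only pharmacodynamic evidence is compromised.** The protocol synopsis marks pharmacodynamics as not applicable and lists the biomarkers among the efficacy variables.
- **That low values are set too low by a factor of d.** Any value under the reported limit is possible, and half of it is only a convention.

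**Conclusion.** The rule is wrong as written at the high end. For any dilution factor above 1.5 it assigns a value that contradicts the reported result, and nothing elsewhere in the SAP or protocol repairs it. At the low end there is only an inconsistency of convention.

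The ratios follow directly from the text; the practical size does not. The dilution factors, assay limits and share of over-range samples are all absent from the documents, so the effect could be nil. The geometric-mean figures are illustrations resting on assumed values of d and s. The affected outputs are exploratory descriptive tables; the primary endpoint, sample size and power are untouched. Severity is minor.

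**What to change.** Reword the imputation sentence in SAP 8.6.4.4 so that it works from the reported limit: 0.5 x (LLOQ x dilution factor) for results reported below it, and 1.5 x (ULOQ x dilution factor) for results reported above it. Each high-end value is then 1.5 times the bound it must exceed, and each low-end value is half of its reported limit. With d = 1 nothing changes.

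The cost is one sentence. The reported result already contains the factor, so no new laboratory data are needed; the analysis dataset should keep the reported limit or the dilution factor so that the derivation can be checked.

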8.6.4.5 Change from Baseline in mMRC dyspnoea scale over time

This exploratory endpoint will be analysed separately during the Acute Exacerbation Phase (from Study Day 1 until Day 14 included) and the Stabilisation Phase (from Day 14 until Week 26).

The mMRC dyspnoea scale (graded from 0 to 4) will be summarised at each visit by treatment regimen using descriptive statistics. Changes in mMRC dyspnoea scale from baseline (Visit 1 pre-dose) will be summarised at each post-baseline visit (Day 7 and Day 14) during the Acute Exacerbation Phase by treatment regimen. Changes in mMRC dyspnoea scale from baseline (Visit 9, Day 14) will also be summarised at each post-baseline visit (Weeks 8, 12 and 26) during the Stabilisation Phase by treatment regimen.

MMRM analysis using an unstructured covariance matrix and the Kenward-Roger adjustment for the denominator degrees of freedom will be performed for statistical comparison of treatment regimens with change in mMRC as an outcome. MMRM analyses will be done separately for the Acute Exacerbation Phase and for the Stabilisation Phase. Both models will consider treatment, severity of airflow limitation at baseline (pre-dose), blood eosinophils (%) value at baseline (pre-dose), time from start of current COPD exacerbation to first IMP dosing, presence of cardiovascular comorbidities at screening and COPD exacerbation treatment at screening as fixed effects and baseline mMRC (Visit 1 pre-dose for the Acute Exacerbation Phase, Visit 9/Day 14 for the Stabilisation Phase) as covariate. In addition the baseline mMRC-by-visit and the treatment-by-

visit interactions will be included in the model.

LSMEAN and standard error (SE) of each treatment regimen, difference of LSMEANS between treatment regimens and their associated two-sided 95% CIs and corresponding two-sided P-values for Day 7, Day 14 (Acute Exacerbation Phase) and Weeks 8, 12 and 26 (Stabilisation Phase) will be estimated by the model. P-values of the effects will also be presented.

The unstructured covariance matrix (which does not presume a particular correlation structure for repeated measurements within patients over time) will be used to adjust for the within-patient error variance covariance. In case model fails to converge, other covariance matrix structures will be considered in the sequence of Ante-dependence, Toeplitz, Heterogeneous AR(1), Heterogeneous Compound Symmetry, and Compound Symmetry.

A figure with adjusted mean change from baseline (Visit 1 pre-dose) in mMRC dyspnoea scale at each visit during the Acute Exacerbation Phase by treatment regimen derived from the linear mixed model will be provided. A similar figure with adjusted mean change from baseline (Visit 9/Day 14) in mMRC dyspnoea scale will also be provided for the Stabilisation Phase separately.

8.6.4.6 BODE index at Day 14

A descriptive summary table will be presented for BODE index at Day 14 by treatment regimen. BODE index at Day 14 will be compared between treatment regimens using a one-way ANOVA test, and the associated two-sided p-value will be reported in the summary table.

Should the normality assumptions for BODE index at Day 14 not be met (the skewness and kurtosis measurements will be considered as supportive indicators), the relationship between BODE index at Day 14 and treatment regimen will be tested using the non-parametric approach of Kruskal-Wallis test (or Wilcoxon Rank-Sum test for pairwise treatment regimens).

For the subgroup of patients enrolled in the study under protocols V2.0 and V3.0, a separate descriptive summary table will be presented for BODE index at baseline (Visit 1 pre-dose), Day 7, Day 14, Week 8, Week 12 and Week 26 by treatment regimen. Due to the small number of patients involved, no statistical comparison between treatment regimens will be performed.

8.7 Safety analyses

All definitions relative to safety endpoints are detailed in Section 7.1.5.

All the safety analyses will be based on the Safety population (treated subject) and will be performed for all safety variables specified below.

In order to assess the safety and tolerability of two different dosing regimens of BCT197 added to SoC versus placebo added to SoC in patients with severe acute exacerbations of COPD, all subjects will have routine safety monitoring throughout the study, including TEAEs/SAEs, TEAEs of special interest (pneumonia, rash/acneiform dermatitis/pruritus, cervical/vaginal inflammation,

headache and liver enzymes), 12-Lead ECGs, vital signs, clinical laboratory assessments (haematology, blood chemistry, urinalysis, pregnancy tests) and quantitative sputum cultures.

The safety parameters collected and changes in these parameters from baseline will be summarised for the treatment regimens separately using standard tabulations and listings. The patients who did not receive the treatment planned by the randomisation will be analysed per the treatment received.

No statistical test will be performed.

8.7.1 Adverse events

All AEs will be classified by SOC and PT according to the MedDRA Version 20.0 or higher.

AEs will be classified as pre-treatment AEs or TEAEs. Additionally, TEAEs will be classified as occurring during the Acute Exacerbation Phase (from Study Day 1 until Day 14 included) or occurring during the Stabilisation Phase (after Day 14 until Week 26).

Details for imputing missing or partial start dates of adverse events are described in Section 7.2.2.4.

Acute exacerbations of COPD reported in the ‘Acute Exacerbation COPD’ form of the eCRF will also be included in the analysis of AEs (tables and listings).

Notes:

- Two AEs with the same PT and classified in the same category (pre-treatment AE or TEAE) will be considered as two different events when calculating the “number of events” in the tables.
- Where a subject has the same AE, based on preferred terminology, reported multiple times in the same category (pre-treatment AE or TEAE), the subject will only be counted once at the preferred terminology level in AE frequency tables.
- Where a subject has multiple AEs within the same SOC in the same category (pre-treatment AE or TEAE), the subject will only be counted once at the SOC level in AE frequency tables.

Pre-treatment AEs and TEAEs will be presented separately. Pre-treatment AEs will be presented in the listings only.

An overall summary of AEs will be provided. The total number of events and number and proportion of subjects experiencing any AEs, TEAEs, TEAEs of special interest, AEs related to study medication, SAEs, SAEs related to study medication, severe AEs, AEs leading to permanent discontinuation of study treatment and AEs leading to death will be tabulated for each treatment regimen and overall. This overall summary of AEs will also be provided for TEAEs occurred during the Acute Exacerbation Phase and for TEAEs occurred during the Stabilisation Phase separately.

Additionally, TEAEs, TEAEs of special interest, related TEAEs, serious TEAEs, related SAEs, severe TEAEs, AEs leading to permanent discontinuation of study treatment and AEs leading to

death will be summarised by SOC and PT for each treatment regimen and overall (number and percentage of subjects experiencing at least one AE per PT as well as the number of observed events per PT). All TEAEs will also be summarised separately by maximum severity grade for each SOC and PT and by relationship to study medication for each SOC and PT. These summarisations of TEAEs will also be provided for TEAEs occurred during the Acute Exacerbation Phase and for TEAEs occurred during the Stabilisation Phase separately.

A table presenting the number and percentage of subjects with at least one AE and the number of AEs for the most common treatment-emergent AEs (reported in $\geq 1\%$ of patients in any treatment regimen) will be provided. PTs will be used for tabulation, sorted by decreasing overall frequency. This table will also be presented for TEAEs occurred during the Acute Exacerbation Phase and for TEAEs occurred during the Stabilisation Phase separately.

The number and percentage of subjects with any treatment-emergent pneumonias, pneumonias related to study medication, serious pneumonias, serious pneumonias related to study medication, severe pneumonias, pneumonias leading to permanent discontinuation of study treatment, pneumonias leading to death will be presented by treatment regimen and overall. The number of events will also be displayed. This table will also be presented for treatment-emergent pneumonias occurred during the Acute Exacerbation Phase and for treatment-emergent pneumonias occurred during the Stabilisation Phase separately.

Treatment-emergent pneumonias will be analysed in terms of rate per 1'000 patient per year. The follow-up time (in years) will be calculated using the following formula:

$$(\text{date of last contact} - \text{date of first study treatment} + 1) / 365.25$$

The rate of treatment-emergent pneumonia per 1'000 patient per year will be calculated for each treatment using a weighted approach (which consists of pooling all patients of a treatment regimen and dividing the total number of events by the total follow-up time, multiplying the result by 1000).

All AEs will be presented in full in a comprehensive listing including subject number, treatment regimen, severity, seriousness, actions taken, outcome, relationship to treatment, onset/stop and duration. Details of all AEs (pre-treatment AEs, TEAEs during the Acute Exacerbation Phase and TEAEs during the Stabilisation Phase separately), TEAEs of special interest, SAEs, AEs leading to permanent discontinuation of study treatment and AEs leading to death will be listed separately.

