A preplanned interim analysis of Part B was conducted in October 2013 which included 66 subjects who had completed Day 5. At that time the AKI rate was higher on BCT197 [6/31 (19%)] than on placebo [2/33 (6%)], whereby AKI was defined as 25% or more reduction in eGFR at 48 hours. The reported (expected) control rate of AKI is in the 10 to 20% range. None of the subjects required dialysis. Furthermore, the number of subjects reporting SAEs in the BCT197 group [12 (36%)] was higher than that on placebo [3 (9%)], but these were distributed over several types of SAEs that were also expected in the cardiopulmonary bypass population. None of the SAEs was related to a kidney disorder and none was suspected to be related to study medication. The BCT197 group had an average baseline weight 9.1 kg heavier than the placebo group, suggesting that there may have been some degree of unbalanced randomisation. Based on the IA data, the Data Monitoring Committee (DMC) recommended to put the study on hold for reasons of lack of efficacy and the higher rate of SAEs on BCT197. According to the DMC the data did not allow assessment for a possible nephrotoxicity.

Based on the data available thus far, it appears that a regimen longer than a single dose would be required to sustain the effect of BCT197. Subjects will receive one of two oral dosing regimens of BCT197 or matching oral placebo administered according to the dosing schedules shown in [Table 7-1](#).

BCT197 is intended to be prescribed as a treatment added to standard of care (SoC) of acute exacerbations in COPD and is envisaged to be used for repeated administration. BCT197 is formulated as oral capsules. The two dose regimens proposed for this study are based on the efficacy, toxicology, pharmacokinetic and safety data available thus far. 

The rationales for the dose regimens proposed are based on the PK exposure and are explained in the [Section 7.2](#) below.

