home and/or to allow specific monitoring of the subject due to their unstable medical condition. Current hospitalisation due to the COPD and pre-planned hospitalisations (known already prior to signing the ICF) will not be considered an SAE, unless any of the above criteria are fulfilled over the course of the hospitalisation due to unplanned complications. Following the initial discharge from hospital, subsequent hospitalisations due to COPD are to be considered an SAE. “Social” hospitalisation, defined as administrative impossibility to discharge the subject is not necessarily an SAE. Complications that occur during hospitalisation are AEs unless they would qualify as an SAE for any of the above criteria. If the complication delays the subject’s release from hospital, then the AE becomes an SAE. Hospitalisations due to diagnostic procedures which are not performed due to an AE are not regarded as SAE.

4. Results in persistent or significant disability/incapacity

The term significant disability refers to any condition that impairs physical/psychological well-being to the extent that the subject is unable to function normally. Physical disability may include, but is not limited to, permanent disability of locomotion or motility, but also systemic permanent dysfunction as development of heart failure, liver insufficiency or pulmonary fibrosis.

5. Is a congenital anomaly/birth defect

6. Is an important medical event

Important medical events that may not result in death, be life-threatening or require hospitalisation may be considered an SAE, when based on appropriate medical judgement, they may jeopardise the subject or the subject may require medical or surgical intervention to prevent one of the outcomes listed in this definition.

Treatment Emergent Adverse Event (TEAE)

TEAEs are defined as any AE occurring or worsening on or after the first dose of study medication.

Adverse Events of Special Interest (AESI)

Refer to [Section 12.1.7](#).

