4.2 Secondary efficacy endpoints

The secondary efficacy endpoints of this study are:

1. Comparison of FEV1 on Days 3, 10, and 14
2. Normalisation evaluation of spirometry parameter (FEV1 and FEV1/FVC) response over time (performed daily from Days 1 to 7, 10, and 14, and Weeks 8, 12 and 26) compared with the most recent test performed within the last 12 months outside an exacerbation (pre-study FEV1 and FEV1/FVC value)
3. Time to improvement of 100 mL in FEV1 compared with Baseline versus placebo
4. Comparison of AUC of FEV1 over time among groups
5. Change in RR normalisation over time (performed daily from Days 1 to 7, 10 and 14) among groups
6. Change in RR on Days 3, 7, 10 and 14 among groups
7. Time to improvement based on EXACT-PRO total score
8. Comparison of AUC of EXACT-PRO over time among groups
9. Number of COPD-related deaths during the study
10. Number of moderate/severe COPD-related exacerbations during the study
11. Time to next moderate/severe COPD exacerbation
12. Change from baseline at each inter-visit period and over the entire period of the study in the average EXACT-PRO total score and domain scores
13. Number of times each subject required rescue therapy during the study
14. Time from hospitalisation admission until the subject is medically ready (COPD-related) for discharge
15. Nonlinear mixed effects pharmacokinetic/pharmacodynamic (PK/PD) models evaluating the relationship between BCT197 exposure and efficacy/safety endpoints.

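### SAP 8.7.1 counts COPD exacerbations as adverse events and plans no subject-level summary without them, so the whole-study and Stabilisation Phase any-SAE and any-TEAE rows mix efficacy with safety

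*SAP*

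**What the plan says.** SAP 8.7.1 adds exacerbations reported in the 'Acute Exacerbation COPD' "form of the eCRF will also be included in the analysis of AEs (tables and listings". SAP 4.2 lists among the secondary efficacy endpoints "Number of moderate/severe COPD-related exacerbations during the study", and SAP 8.6.3.11 derives it from the same form. Protocol 12.1.1 adds: "Following the initial discharge from hospital, subsequent hospitalisations due to COPD are to be considered an SAE".

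The overall summary in SAP 8.7.1 gives events and subjects, by regimen, for any AE, TEAE, SAE, related SAE, severe AE, and AE leading to discontinuation or death. It is also split by phase: "This overall summary of AEs will also be provided for TEAEs occurred during the Acute Exacerbation Phase", and likewise for the Stabilisation Phase. Serious TEAEs and the other categories, down to AEs leading to "death will be summarised by SOC and PT for each treatment regimen and overall", are tabulated with subject counts "as well as the number of observed events per PT". SAEs are listed individually. For safety as a whole, SAP 8.7 says: "No statistical test will be performed".

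Protocol 7.1 describes the earlier BCT197 trial in cardiac surgery. The number of subjects with SAEs on BCT197, 12 (36%), "was higher than that on placebo [3 (9%)], but these were distributed over several types of SAEs". That trial's monitoring committee recommended a hold, citing lack of efficacy and the higher SAE rate.

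**The concern.** With no safety tests planned, readers will judge general safety from the descriptive any-SAE and any-TEAE rows. In patients enrolled during a hospitalised exacerbation, many of the SAEs over 26 weeks are likely to be COPD readmissions, which the trial also counts as an efficacy outcome. If BCT197 does nothing for exacerbations, a real excess of other SAEs is diluted by a common background event. If it reduces exacerbations, the benefit offsets the excess in the same row.

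The system organ class and preferred term tables do not supply the missing number. Subtracting the COPD term gives non-COPD events, but not the number of subjects with at least one non-COPD SAE, because a subject can appear under several terms. A diffuse excess, as reported in the earlier trial, is best read as a subject count.

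There is also a counting gap. SAP 7.1.4.13 takes COPD deaths from the 'Adverse Event' form and SAP 8.6.3.11 takes them from the 'Acute Exacerbation COPD' form. SAP 8.7.1 counts two AEs with the same preferred term as two events. No rule covers an exacerbation recorded on both forms.

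**Working it through.** **Figure in the documents.** Protocol 7.1 reports 66 subjects at the earlier interim analysis. With 33 per arm (inferred; the SAE denominators are not printed), 12/33 = 36.4% and 3/33 = 9.1%, which match the stated 36% and 9%.

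**Inputs.**
- Non-COPD SAE risk on placebo: 9%, borrowed from the earlier trial.
- Non-COPD SAE risk on active: 18% (an assumed doubling) or 36% (the earlier trial's rate).
- 26-week COPD-SAE risk q: assumed 30%, range 20% to 40%. Protocol 7.1 cites about 60% readmitted for exacerbation within 12 months. With a constant hazard that is 1 − √0.40 = 36.8% at 26 weeks. A 12-month rate of 30% would give 16%, and 80% would give 55%.
- COPD and other SAEs are independent (assumption).

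**Formula.** P(any SAE) = 1 − (1 − q)(1 − p), where p is the non-COPD SAE risk.

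**No effect on COPD SAEs, q = 30%.**
- Placebo: 1 − 0.70 × 0.91 = 36.3%
- Active, p = 18%: 1 − 0.70 × 0.82 = 42.6%
- Active, p = 36%: 1 − 0.70 × 0.64 = 55.2%

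| q | 9% vs 18% reads | Ratio (true 2.0) | 9% vs 36% reads | Gap (true 27 points) |
|---|---|---|---|---|
| 20% | 27.2% vs 34.4% | 1.26 | 27.2% vs 48.8% | 21.6 |
| 30% | 36.3% vs 42.6% | 1.17 | 36.3% vs 55.2% | 18.9 |
| 40% | 45.4% vs 50.8% | 1.12 | 45.4% vs 61.6% | 16.2 |

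**COPD SAEs cut from 30% to 20% on active.** With p = 18%: 1 − 0.80 × 0.82 = 34.4%, against 36.3% on placebo. The doubling no longer shows.

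**Cut needed for complete masking.** The rows are equal when the active COPD-SAE risk is q* = 1 − (1 − q)(0.91)/(1 − p).
- 9% vs 18%, q = 30%: 1 − 0.637/0.82 = 22.3%, a relative cut of about 26%.
- 9% vs 36%, q = 30%: 1 − 0.637/0.64 = 0.5%, almost complete elimination.
- 9% vs 36%, q = 40%: 1 − 0.546/0.64 = 14.7%.
- 9% vs 36%, q = 20%: 0.728/0.64 exceeds 1, so masking is impossible.

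**Share of COPD in the row.** At q = 30%, 0.300/0.363 = 83% of placebo subjects with any SAE have a COPD SAE. Over the range, the share runs from 0.200/0.272 = 74% to 0.400/0.454 = 88%.

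**The case against.** The strongest counter-argument is timing. The earlier excess was seen in subjects who had completed Day 5 after a single dose. Here dosing is on Days 1, 3 and 5, and Protocol 9.3.2 equates five half-lives with 8 days, so exposure is largely over by about Day 13. The overall summary is repeated for Day 1 to 14, where COPD SAEs should be few: the index admission is not itself an SAE, readmissions count only after first discharge, and Protocol 7.1 cites a median stay of 9 to 10 days. A reader might infer that the planned tables would hide an SAE excess like the earlier one. The documents do not support that. An early excess would fall in a row with little contamination, and at the earlier size even the whole-study row keeps a gap of about 19 points at the 30% assumption.

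Second, the information is not lost. Non-COPD SAE events follow by subtraction, subject counts can be rebuilt from the SAE listing, pneumonia has its own table, and SAP 8.6.3.11 shows exacerbations requiring hospitalisation or causing death by regimen. This stands, but a rebuilt subject count would be post hoc, with its exclusion rule chosen after unblinding.

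Third, a COPD readmission is a protocol-defined SAE and worsening COPD could itself be a harm. This also stands: making an exacerbation-free version the main safety comparison would demote those events.

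Finally, the table templates and the monitoring committee's SAP are separate documents not available here, so the statement that no such summary is planned applies to the SAP text only.

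**Conclusion.** The point holds for the whole-study and Stabilisation Phase summaries. Their any-SAE and any-TEAE rows combine an efficacy outcome with safety, and the SAP specifies no subject count that separates them. A moderate non-COPD excess (9% versus 18%) would shrink from a ratio of 2.0 to between 1.12 and 1.26, and could vanish if the drug also reduced COPD SAEs by about a quarter at the 30% assumption. An excess of the earlier trial's size would be diluted but remain visible, and the Day 1 to 14 summary is a partial safeguard for an early one.

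These sizes rest on an assumed COPD-SAE risk, independence of the two kinds of SAE, and a placebo rate borrowed from a cardiac-surgery population. The structural point, that the planned rows mix the two, needs none of these assumptions.

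**What to change.** In SAP 8.7.1 keep all planned tables. Beside them, add pre-specified rows of the overall summary for any TEAE, SAE, related SAE, severe AE, and AE leading to discontinuation or death, with subjects and events, overall and by phase. These rows should exclude events from the 'Acute Exacerbation COPD' form and the matching COPD-exacerbation AEs, with the list of matching preferred terms fixed before unblinding. State that an exacerbation recorded on both forms is counted once. Present both versions with equal standing and do not name either as the main comparison. The cost is one extra set of tables from data already collected.
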